5.0 STATISTICAL CONSIDERATIONS

5.1 Outcome Measurements

None of the listed outcomes relate to safety.

Primary Outcome Measure

The specific key measurement used to measure the effect of the intervention corresponding to the primary outcome is change in health-related quality of life. The protocol aims primarily to detect a significant (5% significance level) between-group difference from baseline to 4 months (delta

change=4) assuming a within-subject correlation of 0.8 and a standard deviation of the change in score equal to 9.5 based on empirical evidence.

Secondary Outcome Measure

Patient satisfaction and activation will be explored using changes in the Patient Satisfaction with Decision Scale and Patient Activation Measure. Utilization will be measured evaluating comparisons of hospitalizations, emergency department, and referrals to hospice and palliative care. Advanced care planning will be measured by comparing rates of advance directive documentation, Physician Orders for Life-Sustaining Treatment, and goals of care documentation in patients' electronic health record charts. Patient survival will also be compared between groups. Total costs of care will be abstracted from UHH database only to conduct a budget impact analysis and obtain point estimates for refinement of the intervention in anticipation of a larger multi-center trial. A cost-effectiveness analysis is not planned and will not occur until effectiveness has been demonstrated in subsequent studies upon completion of this study.

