3.2 Participant Criteria

Inclusion criteria

1. Newly diagnosed patients with a cancer diagnosis.
2. Patients with any relapse or progressive disease (any cancer diagnosis) as identified by imaging or biopsy and confirmed by physician.
3. The patients must be 18 years or older.
4. Patients must have the ability to verbally consent and understand study procedures.

Exclusion Criteria

1. Inability to consent to the study.
2. Patients without a newly diagnosed malignancy or patients without relapse of disease.
3. Patients not eligible for fund benefits.

Criteria for Removal from Study

Any patients or families of patients in the intervention arm who withdraw consent will be removed from the study. Upon removal, usual care will be restored for these patients.

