4.0 MATERIALS AND METHODS

After a patient is enrolled in the study, the patient will be registered and entered into the project database (CarMa) and assigned an identification number. The identification number will be used on all subject-specific documents and research-related forms.

During registration, patients will be randomized to two arms (Arm A: Usual Care or Arm B: LEAPS Intervention). Specifically, the patients will be randomized 1:1 using a simple randomization strategy in each site into two arms at each site.

All patients, throughout the study, will be asked to complete three surveys: 1) patient health-related quality of life (using Functional Assessment of Cancer Therapy – General (FACT-G) and 2) satisfaction with decision-making (Satisfaction with Decision Scale) and 3) the patient activation measure (Patient Activation Measure-13). A trained study staff member will administer the surveys at baseline (month 0) and again at 4 months and 12 months for patients in the intervention and usual care arm. Participant information will be entered into the CarMa database within 7 calendar days. Study team members will conduct electronic health record chart review of each participant and abstract date of the following: goals of care documented by oncology clinician, advance directive, and Physician Order for Life Sustaining Treatment. All health care claims data will be provided by UHH to the study team for each participant in the study at the study end which will consist of all charges and paid claims for total costs including outpatient, inpatient and pharmacy services. All study team members will be blinded to the randomization assignment. Only the community health workers will know the study assignment and the local site coordinator at each site.

As part of usual care, study PI and team members redesigned benefits such that any member of UHH with cancer will also receive waived copays if they choose to seek care at the preferred

provider in Atlantic City. We will also provide each member with access to transportation and other services to receive care at the preferred provider.

- Arm A: Usual Care (Control) / No Intervention

Patients in this arm receive “usual” care coordination from their care coordination team which includes case management by a registered nurse practitioner to address financial concerns, care navigation and coordination.

- Arm B: LEAPS/ Intervention Group

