The FACT-G is a quick, validated, 27- item compilation to assess QOL domains with discriminate ability and sensitive to changes in QOL over time.

The Satisfaction with Decision scale is a quick, validated 6-question survey to assess patient experiences with decision-making.

The Patient Activation Measure is a validated measure used to assess patient activation.

[name] has used these measures with success in a similar project completed at the Palo Alto Veterans Hospital (Palo Alto, CA). Unite Here Health uses Patient Activation Measure as part of usual care at their organization.

If patients feel discomfort while conducting their surveys, they may choose to not complete them. If there are any psychological events that occur during the study, these will be reported to the site PI.

Site PI: [name]/[name]

[name]/[name] are responsible for overall study supervision as well as the following:

Conducting biweekly meetings with all study staff members, troubleshooting recruitment and follow-up challenges, participating in the training of the CHWs, ensuring proper data collection, and general upkeep. The site PI is also responsible for interacting with the protocol director at Stanford, [name]. As this is [name] conception, and she piloted at another site, she will be able to provide [name]/[name] with specific advice and recommendations should challenges arise.

Protocol Director: [name]

[name], PI of the study, is responsible for the overall study including corresponding with the site PI to help troubleshoot any challenges in data collection or follow-up. [name] is also responsible for assisting the sites in implementing the intervention, following study protocols, and responsible for conducting and overseeing data analysis and manuscript publication.

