5.2 Analysis Plan

The Statistical Analysis Plan (SAP) will be prepared prior to the commencement of data analysis. All patients enrolled in the study will be used for the analysis for an intention to treat analysis.

Secondary analyses are for exploratory outcomes only and include differences in satisfaction with decision-making, acute care utilizations and to obtain point estimates on costs of care. Statistical significance of secondary outcomes is for trends only and not represented in this sample size calculation.

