1.1. Study Aims

1.1.1. Aim 1

The primary aim of the LEAPS program is to evaluate whether trained lay health workers who engage newly diagnosed patients with cancer and patients with newly diagnosed relapsed or progressive disease can improve Health-Related Quality of Life (HrQOL) at 4 months post-enrollment compared to baseline more than usual care.

1.1.2. Aim 2

Secondary aims which a priori defined to be exploratory include the effect of the intervention on changes in health-related quality of life from baseline to 12-months post-enrollment as compared to usual care, changes in patient satisfaction with decision-making and patient activation at 4- and 12-months post-enrollment as compared to baseline, change in emergency department and hospital use within 4- and 12-months post-enrollment, advance directive, goals of care documentation, and Physician Orders for Life Sustaining Treatment documentation at 4- and 12-months post-enrollment, and hospice and palliative care use within 4- and 12-months post-enrollment and total costs of care from baseline to death or 12-months follow-up, whichever is first. In addition, we will evaluate emergency department, hospitalization, hospice and palliative care use and total costs of care in the last 30 days of life among those who died.

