3.2 Secondary Outcome(s) – Exploratory Outcomes Only

Health Related Quality of Life is measured by the Functional Assessment of Cancer Therapy-General: a 27-item questionnaire designed to measure four domains of HRQOL in patients with cancer. The scale is on a 5-point Likert-type scale with a score range of 0-108 with higher scores indicating greater HRQoL.

Patient Satisfaction with Decision is measured by the Satisfaction with Decision scale, a six-item scale designed to measure patient satisfaction with healthcare decision. Each item is on a 1-5 scale with higher scores indicating greater satisfaction with decision.

Patient activation is measured by the Patient Activation Measure. Each item rated on 4-point scale (1 strongly disagree to 4 strongly agree, with additional “not applicable” option. Total PAM score = [raw score]/[# items answered excepting non-applicable items] *13 ; can be transformed to a scale with a theoretical range 0–100 based on calibration tables. Raw scores can be converted into activation levels which can also be used as cut-offs:

4. Statistical Analysis Plan

We will present descriptive statistics broken out by intervention group for baseline clinical and demographic variables of interest using continuous (mean, standard deviation, median, interquartile range), and discrete (counts, percentages) where appropriate. We will also tabulate and present for each relevant covariate the percentage of subjects missing a value for that covariate, if applicable.

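### Satisfaction with Decision: comparing the 4- and 12-month scores adjusted for month 0 would be more precise than comparing change, and easier to read because the rated decision is not specified

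*Combined protocol and SAP*

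**What the plan says.** **Form of the outcome.** Protocol 5.1, under Secondary Outcome Measure, states: "Patient satisfaction and activation will be explored using changes in the Patient Satisfaction with Decision Scale and Patient Activation Measure". SAP 1.1.2 lists "changes in patient satisfaction with decision-making and patient activation at 4- and 12-months post-enrollment as compared to baseline".

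**Timing.** Protocol 4.0: "A trained study staff member will administer the surveys at baseline (month 0) and again at 4 months and 12 months". This applies to both arms.

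**What is rated.** SAP 3.2 calls the instrument "a six-item scale designed to measure patient satisfaction with healthcare decision". Protocol 4.0 describes it more loosely as a "6-question survey to assess patient experiences with decision-making". Neither names the decision, says whether it is the same at each visit, or says how a patient with no decision to rate should answer.

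**Who is rated.** Protocol 3.2 admits two groups: "Newly diagnosed patients with a cancer diagnosis" and "Patients with any relapse or progressive disease (any cancer diagnosis) as identified by imaging or biopsy and confirmed by physician". There is no rule on whether a treatment decision has already been taken.

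**Model and status.** The only model in the SAP, the GEE in 4.2.1, is written for the primary outcome. Protocol 5.2 places this scale among the exploratory outcomes: "Statistical significance of secondary outcomes is for trends only and not represented in this sample size calculation".

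**The concern.** A change score is easiest to read when both visits measure the same thing. FACT-G and the Patient Activation Measure describe the patient's own state, so their month-0 level has a plain meaning. A scale that rates a decision depends on which decision the patient has in mind. At entry, a newly diagnosed patient may be thinking of a different decision from the one in mind at 4 or 12 months, or may have none to rate. The plan does not settle this.

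Two things are at stake, both modest. The first is interpretation: if the decision differs between visits, a rise or fall in the score is not clearly an improvement or a decline. The second is precision: subtracting a weakly related baseline adds its noise to the comparison, whereas using it as a covariate takes from it only what helps.

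**Working it through.** **Inputs.** From the documents: 160 patients, 80 per arm (SAP, Sample Size Considerations); surveys at months 0, 4 and 12 (protocol 4.0); 5% significance level (protocol 5.1, stated for the primary outcome; taken here as two-sided). The documents give no SD, correlation or effect size for this scale, so there is no figure of the plan's own to reproduce. The correlation of 0.8, the SD of change of 9.5 and the power above 90% belong to FACT-G and are not carried over as facts. I let r range from 0.1 to 0.8 as an assumption.

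**Variance.** Take one visit's variance as 1, equal at both visits, with the same r in each arm. Per patient:

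- change from month 0: 2(1 − r)
- follow-up score alone: 1
- follow-up score adjusted for month 0: 1 − r²

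Adjusted relative to change: (1 − r²) / [2(1 − r)] = (1 + r)/2, which is below 1 for every r below 1.

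**Power, for illustration.** Assume a difference of 0.5 SD and complete data on 80 per arm. With V the variance above, power = Φ(0.5/√(2V/80) − 1.96). For change at r = 0.3: √(2 × 1.4/80) = 0.187; 0.5/0.187 − 1.96 = 0.71; power 76.2%.

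| Assumed r | Variance: change | Follow-up only | Adjusted | Adjusted ÷ change | Power: change | Follow-up only | Adjusted |
|---|---|---|---|---|---|---|---|
| 0.1 | 1.8 | 1 | 0.99 | 0.55 | 65.4% | 88.5% | 88.8% |
| 0.3 | 1.4 | 1 | 0.91 | 0.65 | 76.2% | 88.5% | 91.2% |
| 0.5 | 1.0 | 1 | 0.75 | 0.75 | 88.5% | 88.5% | 95.5% |
| 0.8 | 0.4 | 1 | 0.36 | 0.90 | 99.9% | 88.5% | >99.9% |

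**Reading the table.** Against the follow-up score alone, change loses when 2(1 − r) > 1, that is r < 0.5. It ties at 0.5 and wins above it. Against the adjusted comparison, change loses at every r shown.

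**Unequal SDs.** With SDs s₀ at month 0 and s₁ at follow-up, the variance of change minus the adjusted variance is s₀² + s₁² − 2r·s₀·s₁ − s₁²(1 − r²) = (s₀ − r·s₁)², which is never negative. The sizes in the table move, but the direction does not.

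**Bias.** In 4,000 simulated trials of 80 per arm at each of r = 0, 0.2, 0.5 and 0.8, with a true difference of 0.5 SD, the mean contrast in change lay between 0.496 and 0.505. Its spread fell from 0.229 at r = 0 to 0.099 at r = 0.8, against 0.162 and 0.095 for the adjusted contrast. Change is noisier, not biased.

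**The case against.** A reader might infer that the month-0 decision is a different one from that rated later, or does not yet exist. The documents do not say so. Protocol 4.0 allows the scale to be read as covering experience of decision-making in general, in which case a month-0 level exists and change has a meaning. Patients are found through claims data, inpatient reports and referrals (protocol 3.1), so many are already in care, and those with relapsed or progressive disease are likely to have earlier decisions to rate. This objection stands: a mismatch is possible, not shown.

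A reader might also infer that change must be less precise than ignoring baseline. That needs r below 0.5. If r were 0.8, the only correlation in the documents though given for FACT-G, change would have 0.4 times the variance of the follow-up score alone.

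Nor is it shown that patients without a month-0 score would be lost. No model is stated for this outcome; if the GEE in SAP 4.2.1 were reused, such patients could still contribute their later scores. Its group-by-time contrast at 4 months would, however, still be a difference in change.

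Two further objections also stand. The gain from adjustment is a general one and not peculiar to this scale; what is peculiar is that an unspecified decision makes a low r more plausible, and hence a larger gain. And moving to follow-up scores does not name the decision being rated at 4 or 12 months either.

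None of this touches the comparison of adjusted analysis with change, which holds whatever r is.

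**Conclusion.** The point holds in conditional form. The plan analyses change from month 0 on a scale whose rated decision is not specified. If that decision differs between visits, change is harder to interpret, and if r is below 0.5 it is less precise than the follow-up score alone. Whether either happens cannot be told from the documents.

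What does not depend on this is that adjusting for month 0 gives (1 + r)/2 times the variance of change: a reduction of 45%, 35%, 25% and 10% at assumed r of 0.1, 0.3, 0.5 and 0.8. These sizes rest on equal SDs at the two visits and the same r in both arms.

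It would be wrong to read this as a biased result. Both arms give a month-0 score, and the contrast between randomised arms is unbiased under either analysis, provided the month-0 answers are not affected by allocation. The outcome is exploratory and outside the sample size calculation, so this is a free improvement with no bearing on the primary result.

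**What to change.** In protocol 5.1 (Secondary Outcome Measure) and SAP 1.1.2, define this outcome as the Satisfaction with Decision score at 4 months and at 12 months, compared between arms with the month-0 score as a covariate. Where the month-0 score is absent, enter a constant and add a missing-baseline indicator, so that the patient stays in the analysis. Report the arm difference with its confidence interval at each visit.

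The cost is a few lines of wording for one exploratory outcome. The month-0 score is already to be collected, so no new data are needed. The change should be made before data analysis begins, by which time protocol 5.2 already requires the SAP to be prepared.

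Stating which decision is rated at each visit would help interpretation, and a tick at month 0 for patients with no decision yet could be added. Both are optional, the tick would be new data, and the gain in precision depends on neither. This point asks for no change to FACT-G or the Patient Activation Measure.

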5.2 Analysis Plan

The Statistical Analysis Plan (SAP) will be prepared prior to the commencement of data analysis. All patients enrolled in the study will be used for the analysis for an intention to treat analysis.

Secondary analyses are for exploratory outcomes only and include differences in satisfaction with decision-making, acute care utilizations and to obtain point estimates on costs of care. Statistical significance of secondary outcomes is for trends only and not represented in this sample size calculation.

5.3 Sample Size

The primary goal is to improve quality of life. A total of 160 patients are needed to attain significant between-group differences from baseline to 4 months after study enrollment for patients. (See Primary Outcome Measure section above).

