3.3 Enrollment

The target number of subjects at the site is 160 (80 per arm). Patient enrollment will continue until sample size is reached (anticipated 24 months). Data collection will occur at baseline and months 4 and months 12 for each patient in the study. The data follow-up period (to assess utilization) will occur for up to 12 months following each patient enrollment or death (whichever is first).

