4.2.2.1. Site-specific Modeling

We will consider refitting primary models for each site separately to explore the effect of site heterogeneity on our results.

Sample Size Considerations

The sample size of 160 participants (80 randomized to the intervention group and 80 randomized to the control group) provides greater than 90% power to detect difference in quality of life between groups (delta change =4) assuming a within-subject correlation of 0.8 and a standard deviation of the change in score equal to 9.5 based on our pilot data. The primary outcome was determined by our community partners.

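### The stated power counts all 160 randomised patients as having a 4-month change score; with the SD as labelled it fails even without loss, and attrition lowers it further

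*Combined protocol and SAP*

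**What the plan says.** The primary outcome is the change in FACT-G from baseline to 4 months (SAP 3.1). Protocol 5.1 sets the test: "The protocol aims primarily to detect a significant (5% significance level) between-group difference from baseline to 4 months". Protocol 5.3 gives the number: "A total of 160 patients are needed to attain significant between-group differences from baseline to 4 months after study enrollment for patients". Protocol 3.3 sets the target at 160, 80 per arm, and closes recruitment there: "Patient enrollment will continue until sample size is reached (anticipated 24 months".

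The SAP's Sample Size Considerations take 80 randomised per arm and state that this "provides greater than 90% power to detect difference in quality of life between groups". The target is a 4-point difference in change, and the correlation between one patient's scores is put at 0.8. The spread is given an explicit label: "a standard deviation of the change in score equal to 9.5 based on our pilot data". Protocol 5.1 gives the same difference, correlation and SD.

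The protocol also names ways in which a month-4 score can be lost:

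- Section 4.0, on the surveys: "If patients feel discomfort while conducting their surveys, they may choose to not complete them".
- Section 3.2 removes intervention-arm patients who withdraw consent, or whose families do.
- Section 3.3 ends follow-up at death if that comes first.

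Neither document gives an expected loss, an expected number with month-4 data, or a method for missing month-4 scores. The intention-to-treat statements (protocol 5.2, SAP 4.2) fix the arm in which a patient is analysed; they do not supply a missing score.

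**The concern.** A change from baseline to month 4 is observed only when both scores exist. The number randomised and the number behind the power figure are the same 160, so the calculation implicitly has every patient contributing a change. The documents do not say this outright; it follows from using 80 per arm with no attrition input.

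Some month-4 scores will be missing in a population that includes relapsed and progressive cancer, so the stated power describes a fuller data set than the design is likely to yield. Readers will set a non-significant 4-month result against a claim of more than 90% power, and may take it as stronger evidence against LEAPS than it is. How much this matters depends on what the 9.5 refers to.

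**Working it through.** **Inputs.** Difference in change 4, SD 9.5, correlation 0.8, 80 per arm (SAP Sample Size Considerations; protocol 5.1); alpha 5% (protocol 5.1). Sidedness is not stated; two-sided is assumed. Loss by month 4 is not given; 10%, 20% and 30%, equal in both arms, are assumed for illustration.

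**Formula.** Two-sample t-test on change scores with n pairs per arm: SE = SD × √(2/n), noncentrality = 4/SE, 2n − 2 degrees of freedom.

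**Step 1: the plan's own figure.**

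- As labelled, SD of change 9.5: SE = 9.5 × √(2/80) = 1.502; noncentrality 4/1.502 = 2.66; power 75.4% (75.9% by normal approximation). The stated figure is not reproduced. A one-sided test gives 84.6%, and baseline adjustment 80.2% (both normal approximation); neither reaches 90%.
- If 9.5 is the SD of a single score: SD of change = 9.5 × √(2 × (1 − 0.8)) = 6.01; SE = 6.01 × √(2/80) = 0.950; noncentrality 4/0.950 = 4.21; power 98.7%. This is consistent with the stated figure. It would also explain why a correlation is quoted, since none is needed once the SD of change is known.

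**Step 2: loss of month-4 pairs.** Pairs per arm = 80 × (1 − loss). The SE rises by 1/√(1 − loss).

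| Assumed loss | Pairs per arm | SE ratio | Power, SD of change 9.5 | Power, single-score SD 9.5 |
|---|---|---|---|---|
| 0% | 80 | 1.000 | 75.4% | 98.7% |
| 10% | 72 | 1.054 | 70.9% | 97.8% |
| 20% | 64 | 1.118 | 65.7% | 96.2% |
| 30% | 56 | 1.195 | 59.8% | 93.7% |

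The drop from complete data to 30% loss is 75.4 − 59.8 = 15.6 points as labelled, and 98.7 − 93.7 = 5.0 points on the single-score reading. As labelled, the 95% confidence half-width goes from 1.96 × 1.502 = 2.94 to 3.29 at 20% loss.

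**Step 3: where 90% is crossed.** On the single-score reading, power is 90.4% at 49 pairs per arm and 89.8% at 48, so the claim survives the loss of 31 of 80 per arm (31/80 = 38.75%). As labelled, 90% power would take 119 pairs per arm (normal approximation), so no loss rate rescues or breaks the claim at 80.

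**Step 4: what the planned model recovers.** The GEE in SAP 4.2.1 uses all three visits, so a patient without a month-4 score is not wholly lost. With exchangeable correlation 0.8, ignorable missingness and efficient weighting, the share of the lost variance recovered is:

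- baseline score only: (1 − 0.8)/2 = 0.10;
- baseline and month 12: 1 − [1 − 2 × 0.64/1.8]/0.4 = 1 − 0.289/0.4 = 0.28.

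At 20% loss with SD of change 9.5 (normal approximation), power is 66% from pairs alone, 67% if all the missing have baseline only, and 69% if all return at month 12, against 76% complete. The pair-based figures are therefore slightly pessimistic, but close.

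**The case against.** The strongest reply is that attrition never changes the truth of the stated claim at the loss rates considered. On the single-score reading, power is above 90% with and without loss, and 160 already carries a wide margin, although the documents do not present it as an allowance. On the labelled reading, the claim fails before anyone is lost. This stands. A reader might infer that ignoring attrition is what makes the power statement wrong, or that 160 must be inflated for dropout. The documents support neither: the meaning of 9.5 decides the matter, and inflating 160 for dropout would only preserve 75% if 9.5 is the SD of change.

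Further points stand in part:

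- The withdrawal rule is written for the intervention arm only, so it does not show equal loss in both arms. Equal loss is an assumption here.
- Outcomes planned for the last 30 days of life concern deaths over follow-up to 12 months and say little about deaths by month 4. Newly diagnosed patients of any stage are also eligible, and staff administer the surveys. Nothing in the documents supports the upper end of the 10–30% range.
- The documents state power, not a standard error or interval width, so no stated precision is contradicted.
- The GEE uses partial data, so pair-based power is approximate; Step 4 shows that the recovery is modest.
- The observed confidence interval will reflect actual loss. That protects a careful reader of the results but does not correct the planning statement.

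**Conclusion.** The point holds in a limited form. The power statement and the 160 described as needed both treat every randomised patient as contributing a 4-month change, with no allowance for losses that the protocol foresees. As labelled, power is about 75% with complete data and about 71%, 66% and 60% at 10%, 20% and 30% loss. If 9.5 is a single-score SD, it is about 99%, then 98%, 96% and 94%.

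Attrition is thus a secondary contributor, costing about 4 to 16 points in the first case and 1 to 5 in the second; the SD label determines whether the stated power is right. These figures assume a two-sided 5% test, equal and ignorable loss in the two arms, and complete-pair analysis as an approximation to the GEE. The loss rates are assumptions, not figures from the documents. The point is worth correcting because it is cheap and because the power figure will be used to interpret a null result.

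**What to change.** In protocol 5.1 and 5.3 and in the SAP's Sample Size Considerations:

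1. First state whether 9.5 is the SD of the change or of a single score. The power cannot be restated until this is settled.
2. Keep 160 as the number randomised. The SAP already describes it so; protocol 5.3 should use the same description.
3. Give the expected number of patients with both baseline and month-4 FACT-G, with the loss assumed: for example, 64 per arm at 20%.
4. Restate the power for that number, noting that it is approximate because the GEE also uses partial data.

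The cost is a sentence or two in each document. This fix needs no extra patients and no change to procedures or analysis. The one downside is a less favourable stated power if 9.5 proves to be the SD of change; if it is a single-score SD, the claim of more than 90% still stands at 20% loss.
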